6.2.2. Rescreening

Patients who do not meet eligibility criteria may rescreen once only after approval by the Sponsor or designee.

- If rescreening is performed during the screening window (day -37 to day -8) assessments that did not meet the eligibility criteria must be repeated and completed prior to the pre-randomization visit. If repeat assessments are completed after the end of the screening window but prior to the pre-randomization visit, then all screening procedures must be repeated with the exception of imaging. Imaging assessments (X-rays and MRIs) need to be repeated only if they were done >60 days from the date of the original screening X-rays and MRI.
- If rescreening is performed during the pre-randomization period, all screening procedures must be repeated with the exception of imaging. Imaging assessments (X-rays of the knees, hips, shoulders, and lumbar spine, if applicable, and MRIs) need to be repeated only if they were done more than 60 days from the date of the screening X-rays and MRI.

- If rescreening is performed after the screening window and pre-randomization period end, patients must re-consent and all screening procedures must be repeated with the exception of imaging. Imaging assessments (X-rays of the knees, hips, shoulders, and lumbar spine, if applicable, and MRIs) need to be repeated only if they were done more than 60 days from the date of the screening X-rays and MRI.

6.2.3. Pre-Randomization Visit (Day -7 [+3])

Patients who complete screening and meet the initial eligibility criteria will return to the site to undergo diary training for recording their daily LBP score and use of paracetamol/acetaminophen through the week 16 visit, and for completion of the remaining assessments per the schedule of events. Patients will be instructed to stop using all prohibited medications. During the pre-randomization period, patients may take study-provided rescue medication in the event of inadequate LBP relief, per [Section 5.2](#). Rescue medication must be discontinued 48 hours prior to the baseline/randomization visit.

6.2.4. Baseline/Randomization Visit (Day 1)

If a patient has met all screening eligibility criteria, study sites will complete the procedures as detailed in the schedule of events for the baseline visit. The patient reported outcomes assessments at this and subsequent visits should be completed prior to all other assessments. All laboratory samples at this and subsequent visits must be collected and all study procedures must be performed before study drug is administered. At dosing study visits, urine pregnancy testing will be done and read before the study drug is administered. In the event of a positive urine pregnancy test result, the patient should have a serum pregnancy test with a negative result in order to continue study participation. If the serum pregnancy test is positive, the patient should be withdrawn from study drug and should be asked to return to the clinic for all remaining study visits per the visit schedule (see [Section 6.2.7](#)).

The date of the first dose of study drug is designated as day 1. All subsequent visits should be scheduled based on this date.

6.2.5. Weeks 1 through 16

Complete visits and assessments are outlined in the schedule of events ([Table 1](#)). The patient reported outcomes should be completed prior to all other assessments. All study procedures should be completed before administration of study drug. The last dose of study drug is administered at week 12. Patients who discontinue study drug should return for the remaining study visits, if possible. If patients are not able to continue study participation, they should return for an early termination visit, at which the treatment-period early termination visit assessments will be performed per the schedule of events.

At dosing study visits, urine pregnancy testing will be done and read before the study drug is administered. Study drug will be withheld in the event of a positive urine pregnancy test result. In the event of a positive urine pregnancy test result, a serum pregnancy test must be performed. If the serum pregnancy test is negative, the patient may continue study participation. If the serum pregnancy test is positive, the patient must be permanently discontinued from study drug and should be asked to return to the clinic for all remaining study visits per the visit schedule ([Section 6.2.7](#)).

6.2.6. Weeks 20 through 36

Complete visits and assessments are outlined in the schedule of events ([Table 2](#)). The patient reported outcomes should be completed prior to all other assessments. If patients are not able to continue study participation, they should return for an early termination visit, at which the follow-up period early termination visit assessments will be performed, per the schedule of events.

6.2.7. Early Termination Visit (as Applicable)

Patients who discontinue study drug should be encouraged to continue participation in the study. Patients who are willing to continue do not need to complete an early termination visit and will be asked to participate in all remaining scheduled site visits and telephone contacts through week 36. Assessments should be completed according to the schedule of events ([Table 1](#) and [Table 2](#)). If patients decline to return to the study site for an early termination visit they should be contacted by telephone to collect any safety information.

If patients decline to return to the study site for their scheduled week 16 visit, they should be contacted by telephone to collect any safety information.

6.2.8. Visits in the Event of Total Joint Replacement Surgery

In the event that a patient must undergo TJR surgery during the study, the patient will complete the early termination visit (week 16 or week 36 assessments as outlined in Section 6.2.7) and the procedures outlined in the schedule of events for TJR follow-up ([Table 3](#)). The early termination visit should be completed before TJR surgery if at all possible. All patient-reported pain outcomes should be completed before the physical examination.

6.2.9. Unscheduled Visits

All attempts should be made to keep patients on the study schedule. Unscheduled visits may be necessary to repeat testing following abnormal laboratory results, for follow-up of AEs, or for any other reason, as warranted.

6.3. Study Procedures

6.3.1. Procedures Performed Only at the Screening Visit, Pre-Randomization Visit, or Baseline/Randomization Visit

6.3.1.1. Informed Consent

All patients must sign and date an Institutional Review Board (IRB)-approved or Ethics Committee (EC)-approved informed consent form (ICF) before any study procedures are performed, per [Section 13.2](#).

6.3.1.2. Medical History

The investigator or designee will take a complete medical history that includes information on concurrent medical conditions and the severity for each condition that has not resolved.

6.3.1.3. Medication History

The investigator or designee will query patients on the medication(s) they have taken for their LBP (medication history), including information on their ability to tolerate the medication, and will record the information on an eCRF for this purpose.

6.3.1.4. Assessment of Childbearing Potential

Each female patient should be evaluated for childbearing potential.

Women will be considered to be of childbearing potential unless:

- They are postmenopausal, or
- They have had a tubal ligation, a bilateral oophorectomy, bilateral salpingectomy, or hysterectomy

In women ≥ 59 years of age, postmenopausal is defined as at least 12 continuous months of spontaneous amenorrhea. In women ≤ 59 years of age, postmenopausal is defined as at least 12 continuous months of spontaneous amenorrhea, with serum follicle-stimulating hormone (FSH) levels >40 IU/L and serum estradiol levels <5 ng/dL (see [Section 6.3.3.10](#)).

6.3.1.5. EDiary Training

When initial patient eligibility has been determined during the screening period, patients will return to the site for a pre-randomization visit. At this visit, patients will be instructed on the use of the NRS for scoring their LBP pain, and they will be trained on the EDiary to report their LBP NRS score and their daily paracetamol/acetaminophen use for LB pain.

6.3.1.6. Reporting Your Pain (Patient Education)

The patient education brochure “Reporting Your Pain” will be used to have an interactive discussion with patients at both the screening and pre-randomization visits to ensure patients understand how to report their pain accurately. At subsequent clinic visits, patients will be asked to review the “Reporting Your Pain” brochure themselves. The “Participating in a Research Study: What You Need to Know” brochure will also be reviewed with the patient at the screening visit to ensure appropriate patient expectations in participating in a clinical trial (see [Section 6.1](#)).

6.3.1.7. Assessment of Peripheral vs. Central Pain

Patients will complete the Assessment of Peripheral vs. Central Pain, a self-reported survey, to evaluate the peripheral versus central nature of their pain at the time points indicated in [Section 6.1](#).

A copy of the assessment is provided in the study reference manual.

6.3.1.8. Assessment of Neuropathic vs. Nociceptive Pain

Patients will complete the painDETECT questionnaire to evaluate the neuropathic versus nociceptive nature of their pain at the time points indicated in [Section 6.1](#). The questionnaire is self-administered and consists of 7 questions that address the quality of neuropathic pain

symptoms. The first 5 questions ask about the gradation of pain on a 6-point Likert scale (0 = never; 1 = hardly noticed; 2 = slightly; 3 = moderately; 4 = strongly; 5 = very strongly). Question 6 asks about the pain course pattern (scored from -1 to 2), and question 7 asks about radiating pain, answered 'yes' or 'no' (scored as 0 or 2, respectively).

A copy of the assessment is provided in the study reference manual.

6.3.2. Efficacy Procedures

6.3.2.1. Daily Low Back Pain Intensity Numerical Rating Score

At the screening visit and the pre-randomization visit, the investigator or designee will record the LBPI NRS score indicating pain over the past 24 hours based on the patient's report. Once initial eligibility is confirmed, from the pre-randomization visit to the week 16 study visit, LBPI NRS scores will be reported by the patient into the EDiary ([Section 6.3.1.5](#)) every day at approximately 6 PM. A copy of the assessment is provided in the study reference manual.

6.3.2.2. Roland Morris Disability Questionnaire

The RMDQ is a self-administered, widely used health status measure for LBP ([Roland 1983](#)). It measures pain and function, using 24 items describing limitations to everyday life that can be caused by LBP. The score of the RMDQ is the total number of items checked – ie, from a minimum of 0 to a maximum of 24. Patients will complete the questionnaire at the time points indicated in [Section 6.1](#).

6.3.2.3. Patient Global Assessment of Low Back Pain

The PGA of LBP is a patient-rated assessment of their current disease state on a 5-point Likert scale (1 = very well; 2 = well; 3 = fair; 4 = poor; and 5 = very poor). Patients will complete the assessment scale at the time points indicated in [Section 6.1](#).

A copy of the assessment is provided in the study reference manual.

6.3.2.4. Short Form (36) Health Survey

The SF-36 is a self-administered survey of general health. It measures 8 domains of health: physical functioning, role limitations due to physical health, bodily pain, general health perceptions, vitality, social functioning, role limitations due to emotional problems, and mental health. It yields scale scores for each of these 8 health domains, and 2 summary measures of physical and mental health: the physical component summary and the mental component summary. Patients will complete the survey at the time points indicated in [Section 6.1](#).

A copy of the assessment is provided in the study reference manual.

6.3.2.5. Medical Outcomes Study Sleep Survey

The MOS Sleep Survey is a self-administered 12-question survey of sleep habits ([Hays 1992](#)). Patients will complete the questionnaire at time points indicated in [Section 6.1](#).

A copy of the assessment is provided in the study reference manual.

6.3.2.6. EQ-5D-5L

The EQ-5D-5L is a standardized measure of health status developed by the EuroQol Group to provide a simple, generic measure of health for clinical and economic appraisal. The EQ-5D-5L, as a measure of health-related quality of life, defines health in terms of 5 dimensions: mobility, self-care, usual activities, pain/discomfort, anxiety/depression. Each dimension has 5 ordinal levels of severity: “no problem” (1), “slight problems” (2), “moderate problems” (3), “severe problems” (4), and “unable to” (5). Overall health state is defined as a 5-digit number. Health states defined by the 5-dimensional classification can be converted into corresponding index scores that quantify health status, which range from <0 for states worse than dead to 1 (full health), anchoring dead at 0. Patients will complete the questionnaire at time points indicated in [Section 6.1](#).

A copy of the assessment is provided in the study reference manual.

6.3.3. Safety Procedures

6.3.3.1. Physical Examination

Patients will have a thorough and complete physical examination including an examination of the knees, hips, and shoulders at the time points indicated in [Section 6.1](#). Care should be taken to examine and assess any abnormalities that may be present, as indicated by the patient’s medical history.

Measurements of patient height and weight should be recorded at the time points indicated in [Section 6.1](#).

6.3.3.2. Vital Signs

Vital signs including temperature, pulse, and respiration will be collected at time points indicated in [Section 6.1](#). Pulse will be measured over a 1-minute period. At visits at which study drug is administered, vital signs should be measured before administration of study drug. If the pulse is less than 45 bpm at any visit after the randomization visit, an ECG with rhythm strip will be obtained to confirm the heart rate and rhythm.

6.3.3.3. Electrocardiogram

A standard 12-lead ECG will be performed at the time points indicated in [Section 6.1](#) with the patient in the supine position for approximately 5 minutes and prior to blood samples being drawn. Heart rate will be recorded from the ventricular rate and the PR, QRS, and QT, QTc intervals will be recorded. The ECG data will be read by a central reading center. Detailed procedures will be provided in a separate manual provided by the central reading center.

6.3.3.4. Joint Pain Questionnaire

A joint pain questionnaire will be completed by the patient at the time points indicated in [Section 6.1](#). For each knee, hip, and shoulder joint, the patient will be prompted to indicate if they have experienced pain.

A copy of the assessment is provided in the study reference manual.

6.3.3.5. Survey of Autonomic Symptoms

Signs and symptoms of autonomic dysfunction will be assessed by the investigator at time points indicated in [Section 6.1](#). If possible, the assessment should be completed by the same person throughout the study.

A copy of the survey is provided in the study reference manual.

6.3.3.6. Assessment of Orthostatic Blood Pressure

An assessment of orthostatic blood pressure will be conducted at the time points indicated in [Section 6.1](#). The assessments should be conducted as per the instructions in the study manual. A patient will be determined to have orthostatic hypotension if any of the following criteria are met:

- If the supine systolic blood pressure is <160 mm Hg, a decrease in either the 1 or 3 minute standing systolic blood pressure of ≥ 20 mm Hg, or a decrease in either the 1 or 3 minute standing diastolic blood pressure of ≥ 10 mm Hg from the supine systolic or diastolic blood pressure
OR
- If the supine systolic blood pressure is ≥ 160 mm Hg, a decrease in either the 1 or 3 minute standing systolic blood pressure of ≥ 30 mm Hg, or a decrease in either the 1 or 3 minute standing diastolic blood pressure of ≥ 15 mm Hg from the supine systolic or diastolic blood pressure
OR
- An increase in either the 1 or 3 minute standing heart rate of >30 bpm from the supine heart rate
OR
- The patient is unable to stand for the standing blood pressure measurements due to dizziness or lightheadedness

If the initial assessment for orthostatic hypotension is consistent with the above definition, the supine and standing blood pressures and/or pulse should be repeated as outlined above, up to 2 more times.

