13. History or presence on imaging of arthropathy (osteonecrosis, subchondral insufficiency fracture, rapidly progressing OA type 1 or type 2), stress or recent fracture, neuropathic joint arthropathy, hip dislocation (prosthetic hip dislocation is eligible), knee dislocation (patella dislocation is eligible), congenital hip dysplasia with degenerative joint disease, extensive subchondral cysts, evidence of bone fragmentation or collapse, or primary metastatic tumor with the exception of chondromas or pathological fractures during the screening period
14. Is scheduled for a joint replacement surgery during the study period
15. Signs and symptoms of carpal tunnel syndrome within 6 months of screening
16. History or presence at the screening visit of autonomic neuropathy, diabetic neuropathy, or other peripheral neuropathy including reflex sympathetic dystrophy
17. Evidence of autonomic neuropathy at the screening visit, as defined in the Survey of Autonomic Symptoms
18. History or diagnosis of chronic autonomic failure syndrome including pure autonomic failure and multiple system atrophy (Shy-Drager syndrome)
19. Poorly controlled diabetes (HbA1c >9.0%) at the screening visit
20. Confirmed elevated screening ALT or AST > 2.5x ULN
21. Resting heart rate of <50 beats per minute (bpm) at the screening, pre-randomization or randomization visits
22. History or presence of 2nd or 3rd degree heart block, 1st degree heart block with abnormal QRS, or bifascicular block by ECG at the screening visit
23. History or presence of orthostatic hypotension as defined in [Section 6.3.3.6](#), at the screening, pre-randomization, or baseline visits

24. Poorly controlled hypertension
 - Systolic blood pressure ≥ 180 mm Hg or diastolic blood pressure ≥ 110 mm Hg at the screening visit
 - Systolic blood pressure of 160 mm Hg to 179 mm Hg or diastolic blood pressure of 100 mm Hg to 109 mm Hg at the screening visit, AND a history of end-organ damage (including history of left ventricular hypertrophy, heart failure, angina, myocardial infarction, stroke, transient ischemic attack (TIA), peripheral arterial disease and moderate to advanced retinopathy [hemorrhages or exudates, papilledema])
25. Congestive heart failure with NY Heart Classification of stage 3 or 4

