7.4.1.2. Sympathetic Nervous System Dysfunction

Sympathetic nervous system dysfunction will be monitored throughout the study through physical examination, AE monitoring, assessment of orthostatic hypotension, and the Survey of Autonomic Symptoms (Section 6.3.3.5). New onset or worsening of signs and symptoms of autonomic dysfunction will be evaluated by the investigator.

In cases where new or worsening symptoms consistent with sympathetic nervous system dysfunction are moderate to severe or are clinically-significant and do not resolve or return to baseline in 2 weeks (or less at the discretion of the investigator), study drug will be withheld and the patient should be referred to a specialist. If the evaluation by the appropriate specialist does not suggest sympathetic nervous system dysfunction, study drug may be restarted.

If a patient is determined to have orthostatic hypotension, study drug should be withheld and the AE should be entered in the eCRF.

If the patient is symptomatic and a clinical explanation for orthostatic hypotension is identified (such as a new medication or dehydration due to exercise or illness, or excessive heat exposure), study drug should be withheld, and the patient should return to the study site for an unscheduled visit in 1 to 10 days for an unscheduled assessment of orthostatic hypotension. If orthostatic hypotension has resolved, study drug may be restarted. If the orthostatic hypotension has not resolved, then study drug should be withheld, and the patient should be referred to a specialist (neurologist or a cardiologist) for evaluation of sympathetic nervous system dysfunction. If the specialist's evaluation does not reveal new onset sympathetic nervous system dysfunction including symptoms of bradycardia (lightheadedness), orthostatic hypotension (lightheadedness on standing), syncope, or absence of sweating in conditions where sweating would be expected, then study drug can be given at the next visit. If the specialist's evaluation does reveal sympathetic nervous system dysfunction, then study drug will be permanently discontinued.

If the patient has asymptomatic orthostatic hypotension, study drug should be withheld, and the patient should return to the study site for an unscheduled visit in 1 to 10 days for an unscheduled assessment of orthostatic hypotension. If the unscheduled assessment does not reveal orthostatic hypotension, then study drug may be continued. If the unscheduled assessment demonstrates

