5.8.5. Analysis of Vital Signs

Vital signs (pulse, sitting blood pressures, orthostatic blood pressure/heart rate, and temperature) will be summarized by baseline and change from baseline to each scheduled assessment time with descriptive statistics. The graphs of mean (or median) value of some vital sign parameter vs. visit will also be plotted.

PCSV summary including orthostatic hypotension will be constructed for on-treatment period, post-treatment period and overall during the study.

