6.2. Data Handling Convention for repeat measurements

Orthostatic Hypotension data

This applies specifically to the data handling of repeat measurements in the assessment of orthostatic hypotension. Per protocol, if the initial vital assessments for orthostatic hypotension is consistent with the definition of orthostatic hypotension, the supine, standing blood pressure or pulse should be repeated up to 2 more times. The guidelines for the repeat assessments are shown below:

Initial Assessment	Repeat Assessment 1	Repeat Assessment 2	Does Patient meet OH criteria	Value to be used in the analysis
Does not meet OH definition	N/A	N/A	No	Initial Assessment
Meets OH definition - repeat	Does not meet definition - repeat	Does not meet definition	No	Repeat Assessment 2
Meets OH definition - repeat	Does not meet definition - repeat	Meets OH definition	Yes, AE of OH reported.	Repeat Assessment 2
Meets OH definition - repeat	Meets OH definition	N/A	Yes, AE of OH reported.	Repeat Assessment 1

Baseline for the assessment of orthostatic hypotension vital assessments uses the last available assessment prior to the start of study drug. Measurements post baseline will not be averaged. Rather frequency counts for patients meeting criteria for orthostatic hypotension will reflect the scenario as shown in the table.

Patient reported outcomes data

Should there be duplicate data entries for PRO diary data, the first entry for the day will be used.

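### SAP 6.2 swaps in a repeat orthostatic reading only when the initial one is positive, which would understate mean postural falls, and the documents lack one common rule for how repeats count

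*Protocol*

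**What the plan says.** **Protocol.** Section 6.3.3.6 lists four criteria joined by OR: a blood-pressure fall with lower supine systolic pressure, a larger fall with higher supine pressure, a heart-rate rise, and inability to stand. It introduces them with "A patient will be determined to have orthostatic hypotension if any of the following criteria are met". After a positive initial assessment, "the supine and standing blood pressures and/or pulse should be repeated as outlined above, up to 2 more times". It does not say whether a repeat confirms or cancels the initial result. For conduct it points elsewhere: "The assessments should be conducted as per the instructions in the study manual".

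Two other sections use the determination. Exclusion 23 (4.2.2) covers "History or presence of orthostatic hypotension as defined in" section 6.3.3.6, at screening, pre-randomization and baseline. Section 7.4.1.2 says: "If a patient is determined to have orthostatic hypotension, study drug should be withheld and the AE should be entered in the eCRF".

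**SAP.** Section 6.2 refers back to the protocol's repeats ("The guidelines for the repeat assessments are shown below") and supplies a rule, which in summary is:

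| Initial | Repeat 1 | Repeat 2 | Counted as orthostatic hypotension | Reading analysed |
|---|---|---|---|---|
| negative | – | – | no | initial |
| positive | negative | negative | no | repeat 2 |
| positive | negative | positive | yes, with AE | repeat 2 |
| positive | positive | – | yes, with AE | repeat 1 |

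Readings are not averaged; "frequency counts for patients meeting criteria for orthostatic hypotension will reflect the scenario as shown in the table". Baseline is the last available assessment before study drug. SAP 5.8.5 then states: "Vital signs (pulse, sitting blood pressures, orthostatic blood pressure/heart rate, and temperature) will be summarized by baseline and change from baseline". It also places orthostatic hypotension in the summary of potentially clinically significant values (PCSV). SAP 4.5.6 restates the four criteria without a repeat rule. The PCSV definition in Appendix 10.2 lists blood-pressure falls only, also without a repeat rule.

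**The concern.** There are two separate issues.

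**The analysed value.** Under SAP 6.2 a reading is discarded only if it met the definition. A negative initial reading is never re-measured. Replacing one tail of a noisy measurement invites regression to the mean: large falls are swapped for readings that are smaller on average, and nothing offsets this at the other end. Mean falls would then be understated. An arm with more large falls would lose more, so the arm difference would shrink too.

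**The count.** A patient whose readings are positive, negative, negative is not a case under SAP 6.2. The protocol text does not settle whether the site should regard that patient as having orthostatic hypotension. SAP 4.5.6 and Appendix 10.2 do not settle it for the tables either. Site determinations, AE entries, the SAP 6.2 count and the PCSV count could differ for the same patient. Orthostatic assessment is one of the routes by which the trial monitors sympathetic nervous system dysfunction, an adverse event of special interest, so the safety tables should agree on who is a case.

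**Working it through.** The documents give no figure to reproduce here, and no distribution for postural falls. The inputs below are therefore assumptions, shown over a range.

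**Inputs**
- Cut-off: systolic fall of at least 20 mm Hg (Protocol 6.3.3.6, supine systolic below 160).
- Replacement rule: the table in SAP 6.2.
- Assumed: normally distributed falls; mean 0, 5 or 10 mm Hg; SD 8, 10 or 12; correlation between same-visit readings 0.3, 0.5, 0.7 or 0.9 (36 combinations, 2,000,000 simulated patients each). Only the systolic criterion and one standing time are modelled.

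**Step 1: shift in the mean fall.**
Shift = P(initial positive) × [mean initial fall among positives − mean analysed fall among positives].

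For mean 5 and SD 10, P(initial positive) = 1 − Φ((20 − 5)/10) = 1 − Φ(1.5) = 6.7%. At correlation 0.5 the shift is 0.0666 × (24.4 − 16.6) = 0.52 mm Hg.

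| Correlation | Initial positive | Confirmed under SAP 6.2 | Share kept | Fall among initial positives: initial → analysed | Shift in overall mean |
|---|---|---|---|---|---|
| 0.3 | 6.7% | 2.0% | 29% | 24.4 → 12.6 | 0.79 |
| 0.5 | 6.7% | 2.9% | 43% | 24.4 → 16.6 | 0.52 |
| 0.7 | 6.7% | 3.9% | 59% | 24.4 → 20.1 | 0.29 |
| 0.9 | 6.6% | 5.2% | 79% | 24.4 → 23.1 | 0.08 |

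Over all 36 combinations the shift runs from 0.01 to 1.73 mm Hg, always toward a smaller fall. It is below 1 mm Hg in 32 of them. The share of initial positives that is confirmed runs from 8% to 86%.

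**Step 2: arm difference.** Assume mean falls of 8 and 5 mm Hg, SD 10, a true difference of 3.0 (4,000,000 simulated patients per arm).

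| Correlation | Difference under SAP 6.2 | Shrinkage | Rate ratio, initial positive | Rate ratio, confirmed |
|---|---|---|---|---|
| 0.3 | 2.69 | (3.0 − 2.69)/3.0 = 10% | 1.7 | 2.3 |
| 0.5 | 2.79 | (3.0 − 2.79)/3.0 = 7% | 1.7 | 2.1 |
| 0.7 | 2.88 | (3.0 − 2.88)/3.0 = 4% | 1.7 | 1.9 |

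Applying the same rule at baseline would offset part of the shift in within-arm change. It would not restore the arm difference, because randomisation makes the baseline shift the same in expectation in every arm.

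**Step 3: the passages side by side, for readings positive, negative, negative.**

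| Source | Result |
|---|---|
| Protocol 6.3.3.6 | not stated |
| Exclusion 23; Protocol 7.4.1.2 | inherit 6.3.3.6, so not stated |
| SAP 6.2 | no; repeat 2 analysed |
| SAP 4.5.6 | four criteria, no repeat rule |
| SAP Appendix 10.2 (PCSV) | blood-pressure falls only, no repeat rule |

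Three further gaps show up. SAP 6.2 has no row for initial positive, repeat 1 negative, repeat 2 not done, although the protocol's wording allows fewer than two repeats. The heart-rate criterion is above 30 bpm in the protocol and at least 30 bpm in SAP 4.5.6. Appendix 10.2 omits the heart-rate and unable-to-stand criteria.

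**The case against.** A reader might infer that protocol and SAP contradict each other, so that eligibility and dosing were run on a different rule from the safety counts. The documents do not show that. In Protocol 6.3.3.6 the word any refers to the four criteria, not to the readings. Ordering a repeat only after a positive result suggests the repeat is meant to matter. The study manual, which is not among the documents, may contain the SAP's rule. SAP 6.2 presents its table as following the protocol and ties the AE to a confirmed result. What stands is silence in the protocol and a risk of divergent practice.

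A reader might also compute that requiring confirmation cuts false positives tenfold. With false-positive probability p per reading, the SAP rule fires with probability p²(2 − p), which at p = 5% is 0.49% against 5%. That needs independent same-visit readings in the same patient. In the central case above, confirmation keeps 29% to 79% of initial positives, a factor of 1.3 to 3.4.

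Nor does confirmation by itself hide an imbalance: in Step 2 the between-arm rate ratio rises.

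The consequences are also limited. Protocol 7.4.1.2 monitors sympathetic dysfunction by four routes (physical examination, AEs, orthostatic assessment, autonomic survey), and SAP 4.5.2 identifies events of special interest by an eCRF tick box, so SAP 6.2 does not set that count. For asymptomatic patients, and symptomatic patients with an identified explanation, 7.4.1.2 provides reassessment in 1 to 10 days and possible resumption. The mean summaries are descriptive. SAP section 1 reports that dosing has ended and that the protocol will not be amended to resume it, so a protocol clarification can change little now.

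These points reduce the size and reach of the problem. They do not remove the one-sided replacement, which is written into SAP 6.2, or the missing common rule for counts.

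**Conclusion.** The point holds in limited form. If the readings chosen in SAP 6.2 feed the SAP 5.8.5 summaries, mean postural falls are understated, usually by less than 1 mm Hg, and an assumed 3 mm Hg arm difference shrinks by about 4% to 10% at same-visit correlations of 0.7 to 0.3. The direction follows from the rule. The size rests on assumed normal systolic falls, one criterion and one standing time, because the documents supply no distribution.

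On counts, the documents support the statement that site determinations, AE entries and SAP tables could disagree for a patient with one positive and two negative readings. They do not support the statement that they will, or that patients were enrolled or dosed under a conflicting rule.

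**What to change.** 1. **Mean summaries.** In SAP 6.2, use the initial assessment for every patient at every visit, baseline included, in the SAP 5.8.5 summaries. Protocol 9.6 already takes the first observation when a visit has more than one laboratory value. Patients with no standing value because they could not stand should be counted separately, so that they do not drop out of view.
2. **Counts.** Report orthostatic hypotension by arm two ways: initial assessment positive, and confirmed on repeat. Use the same definition in SAP 4.5.6, 6.2 and Appendix 10.2. Add the missing row for initial positive, repeat 1 negative, repeat 2 not done.
3. **Reconciliation.** Bring Protocol 6.3.3.6, exclusion 23 and 7.4.1.2 into line with SAP 6.2 on how repeats combine. Which rule governs is for the sponsor's clinical team. With dosing ended, this mainly serves interpretation of the data already collected.

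The cost is SAP wording and one extra table row, from data the plan already collects, before database lock.
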